3.2.2. Exclusion Criteria

- 1. Advanced diabetes (e.g., glycosylated hemoglobin [HgbA1c] >7.5%, and/or glycosuria by dipstick, significant proteinuria [>300 mcg albumin/mg creatinine]), other significant kidney disease, kidney cancer, transplanted kidney, single kidney, kidney surgery within the past 6 months (including cyst drainage or fenestration) or acute kidney injury within 6 months prior to Screening.
- 2. Clinically significant incontinence, overactive bladder, or urinary retention (e.g., benign prostatic hyperplasia).
- 3. New York Heart Association Functional Class 3 or 4 heart failure or other significant cardiac or electrocardiogram (ECG) findings that could pose a safety risk to the participant.
- 4. History of infection with human immunodeficiency virus (HIV) unless the participant is clinically stable and doing well on a non-CYP interacting anti-retroviral therapy (ART) regimen and the participant has not required more than 2 changes in their ART regimen since treatment inception.
- 5. History of clinically significant drug or alcohol abuse in the 2 years prior to Screening Visit 1a.
- 6. Contraindications to or interference with MRI assessments (e.g., ferromagnetic metal prostheses, aneurysm clips, severe claustrophobia, or large abdominal/back tattoos). Investigator should seek MRI safety guidance from the local MRI facility.
- 7. Any malignancy within 5 years prior to Screening except for basal cell carcinoma successfully treated with local therapy or malignancies that are considered by the Investigator not to affect participant survival (after discussion with the medical monitor).
- 8. Medical history or findings that preclude safe participation in the trial or participants who are likely to be non-compliant with trial procedures in the opinion of the Investigator or medical monitor.
- 9. Clinically significant liver disease or impairment or alanine aminotransferase (ALT), aspartate aminotransferase (AST), or total bilirubin values >1.2 x ULN during Screening. Note: This criterion will preliminarily be reviewed at Visit 2 based on Visit 1a and Visit

1b results (if Visit 1b is required). The criterion must be re-evaluated no later than Visit 3 when results for Visit 2 are available.

- 10. Requirement for ongoing diuretic use.
- 11. Participants who are currently taking, or are expected to be taking, strong or moderate CYP3A4 or CYP2C8 inhibitors or inducers including regular use of grapefruit juice, Seville oranges, or St. John's wort. If applicable, there should be a 14-day washout of these treatments prior to Visit 2.
- 12. Prior use of a sodium-glucose cotransporter 2 (SGLT2) inhibitor (e.g., canagliflozin, dapagliflozin, empagliflozin, etc.) within the 2 months prior to Screening Visit 1a or expected need for initiation of treatment with a SGLT2 inhibitor during the study.
- 13. Prior use of a hypoxia-inducible factor prolyl hydroxylase (HIF-PH) inhibitor within the 2 months prior to Screening Visit 1a or expected need for initiation of treatment with a HIF-PH inhibitor during the study.
- 14. Simvastatin at a total daily dose >10 mg or amlodipine at a total daily dose >5 mg.
- 15. Prior use of tolvaptan or lixivaptan within the 2 months prior to Screening Visit 1a.
- 16. Prior use of conivaptan, somatostatin analogs (e.g., lanreotide, pasireotide, octreotide, etc.), metformin (except for diabetes), nicotinamide, bardoxolone, demeclocycline, mTOR kinase inhibitors (e.g., everolimus, sirolimus, etc.) or KetoCitraTM or any beta-hydroxybutyrate (BHB) containing supplements within the 2 months prior to Screening Visit 1a.
- 17. Participants who have taken any investigational drug or used an investigational device within 30 days, or 5 half-lives, whichever is longer, prior to Screening Visit 1a or plan to participate in an interventional trial during the study.
- 18. Hypovolemia on physical examination at Screening.
- 19. Abnormal serum sodium concentration at Screening.
- 20. Positive test results for hepatitis B surface antigen (HBsAg).
- 21. Positive test results for hepatitis C (HCV) antibody (Anti-HCV), with the exception of participants for whom the reflex HCV RNA titer test is negative.
- 22. Known sensitivity or idiosyncratic reaction to lixivaptan and/or its excipients.

3.3. Placebo Run-in/Lixivaptan Titration

Participants who meet the inclusion criteria and none of the exclusion criteria will be enrolled in the study and enter the Placebo Run-in Period. During the Placebo Run-in Period, participants will receive four capsules of single-blind placebo twice daily (BID) approximately 10 hours apart over one week of dosing. Throughout the study, participants will take 4 capsules BID to mask transitions from one study period to the next.

Participants who can tolerate the placebo will enter the Lixivaptan Titration Period. During the Lixivaptan Titration Period, single-blind lixivaptan will be started at Level 1 (50 mg BID) and

will be increased weekly through Levels 2 (100 mg BID), 3 (150mg BID), and 4 (200 mg BID) according to the dosing schedule in Table 1. At the 2 highest dose levels (Level 3 [150 mg BID] and Level 4 [200 mg BID]), there will be an opportunity to reduce the evening (PM) dose to Level 3a (150 mg AM/100 mg PM) or Level 4a (200 mg AM/150 mg PM) if aquaretic effects are problematic in certain participants.

Dose Level	AM Dose	PM Dose
1*	50 mg	50 mg
2	100 mg	100 mg
3	150 mg	150 mg
3a**	150 mg	100 mg
4	200 mg	200 mg
4a**	200 mg	150 mg

Table 1: Dosing Levels during the Titration Period

*Dose Level 1 is for initiation of treatment.

**Participants having difficulty tolerating Dose Level 3 can drop back to 150 mg in the AM and 100 mg in the PM (Dose Level 3a: 150/100 mg).

***Participants having difficulty tolerating Dose Level 4 can drop back to 200 mg in the AM and 150 mg in the PM (Dose Level 4a: 200/150 mg).

Once the maximum tolerated dose is achieved during the Lixivaptan Titration Period, participants will generally stay on that dose for 1 additional week to confirm tolerability. As the maximum duration of the Lixivaptan Titration Period is 6 weeks, participants who require a dose reduction at Week 6 (Visit 9), as a result of emerging tolerability issues, will proceed to the double-blind period on the newly assigned (reduced) dose level without extension of the titration period. Participants who are unable to tolerate the minimum dose for entry into the Double-Blind, Randomized Treatment Period (100 mg BID/ Level 2) will be discontinued from the study.

3.4. Randomization

Once the maximum tolerated dose during the Lixivaptan Titration Period is at least 100 mg BID, the participant will be randomized in 2:1 lixivaptan to placebo ratio to either receive lixivaptan or placebo treatment during the Double-blind, Randomized Treatment Period stratified into 1 of 6 strata by the following stratification factors (determined at time of Screening):

- 1. CKD stage (CKD 2 vs. CKD 3/4)
- 2. Mayo Clinic ADPKD Image Classification (1C, ID, or IE)

3.5. Blinding

This is a double-blind study. Blinding was achieved by means of identical appearance for the capsules for lixivaptan and placebo. The placebo capsule does NOT contain the active ingredient (lixivaptan) but contains the same inactive ingredients as in the investigational

product. Throughout the study, participants will take 4 capsules BID to mask transitions from one study period to the next.

Treatment allocation after randomization will be blinded to all participants, investigators, site personnel, and sponsor employees and representatives except the Independent Data Monitoring Committee (IDMC) and its supporting individuals (e.g., study unblinded biostatistician) and Statistical Data Analysis Center (SDAC). The trial will be unblinded following the locking of the database in Part 1. In addition, all participants will be blinded to study drug (placebo or lixivaptan) during the Placebo Run-in Period and Lixivaptan Titration Period in Part 1.

To maintain study blinding, data that can potentially be used to identify the treatment allocation will NOT be shared with the participant, investigator, clinical sites, sponsor, and CRO until the locking of the database in Part 1 of the study. The set of such data are MRI volumetric calculations and other derived data (e.g., htTKV), urine osmolality data, and PK data after randomization.

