--	--

	
Double-Blind Treatment Period in accordance with Table 2. In order to maintain blinding of the treatment assignment from Part 1, the dose level assignment for Part 2 will continue to be managed by the IRT. The dose-titration schedule for this part of the study is described in Table 2.
 
Maintenance Treatment Period (Visits 30 to 42): Following completion of the Lixivaptan Re-titration Period, participants will continue to receive lixivaptan in the Maintenance Treatment Period for 52 weeks at the same dose achieved at the end of the Re-titration Period. Visits will be performed every 4 weeks (± 5 days) during this period. Assessments at each visit are detailed in the Schedule of Procedures – Part 2.
 
Note: In the event of tolerability issues at any time during the study including the Part 2 Lixivaptan Re-titration Period or during the Maintenance Treatment Period, dosing may be decreased or temporarily stopped. Attempts will be made every 4 to 8 weeks to re-establish the previously achieved dose level at the end of the Double-blind, Randomized Treatment Period of Part 1, if medically appropriate. If study drug is interrupted for longer than 8 weeks, then study drug treatment will be permanently discontinued.
 
Follow-up Period II (Visits 43 to 45): Three visits will occur over a 28-day, study drug-free period following the last dose of lixivaptan in the Maintenance Treatment Period. Serum creatinine and serum cystatin C, to determine eGFR for primary and exploratory analyses, respectively, will be drawn at 3 time points. The first visit (Visit 43) will occur on the 8th day (+ 3 days) after the last dose of lixivaptan, and the last visit (Visit 45) will occur on the 28th day (± 3 days) after the last dose of lixivaptan. Visit 44 must be scheduled to occur at least 24 hours after Visit 43 and at least 24 hours prior to Visit 45. At the final study visit, Visit 45, additional efficacy and safety assessments will be obtained; a post-baseline MRI for assessment of TKV and LV is to be obtained between 25 days and 31 days post last dose of study drug and must be completed prior to or on the same day as all other Visit 45 study procedures.
 
The total duration of participation in the study will be approximately 123 to 131 weeks (up to 71 weeks in Part 1 and up to 60 weeks in Part 2) depending on the length of Screening (3 to 8 weeks), Titration (5 to 6 weeks), and Re-titration (2 to 4 weeks). Note that the study may be interrupted at any time if safety issues identified by an Independent Data Monitoring Committee (IDMC) and sponsor potentially compromise the safety of the participants.

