- d. Vital signs will include sitting heart rate and sitting blood pressure. The same position should be used at each visit (Section 7.3.3).
- e. A brief physical examination will be performed at V35, V42/ET and V45. Additional physical examinations will be performed only for assessment of signs or symptoms reported by the participant that might require further evaluation.
- f. Weight may be measured to assess hydration status as necessary at visits other than those indicated in Table 4.
- g. Routine pregnancy testing for WOCBP will be performed locally on urine. All positive urine results will be confirmed by a serum pregnancy test at the central lab.

- h. The post-baseline MRI scheduled for Visit 45 must be completed between 25 days and 31 days post last dose of study drug and must be completed prior to or on the same day as all other Visit 45 study procedures. Volumetric calculations and other derived data from any post-baseline MRI will NOT be shared with the participant, the investigator, the clinical sites, the sponsor, or the CRO because of the potential for unblinding.
- i. Sampling for analysis of blood chemistry will follow the visit schedule specified in [Table 4](#). Chemistry includes the following parameters: albumin; blood urea nitrogen (urea); calcium; chloride; carbon dioxide (CO₂); glucose; phosphorous; potassium; protein; sodium; uric acid. Serum sodium will be assessed at the time-points specified in [Table 4](#) either as part of chemistry or liver chemistry testing. Liver chemistry includes alkaline phosphatase; ALT; AST; bilirubin (total and direct). Blood samples for serum creatinine and serum cystatin C will be collected for calculation of eGFR in accordance with [Table 4](#). At Visits 43, 44, and 45 every effort should be made to draw blood samples for serum creatinine and serum cystatin C at approximately the same clock time as for Visits 23, 24, and 25 for a given participant. Laboratory test results from samples collected as specified in [Table 4](#) are to be reviewed and assessed.
- j. A single plasma specimen for sparse PK sampling will be obtained at the following visits and time-points: V29/Last Re-titration (1 to 6 hours post-dose), V32 (pre-dose), V35 (6 to 10 hours post-dose), and V38 (any time post-dose). Results from PK samples will NOT be shared with the participant, the investigator, the clinical sites, the sponsor, or the CRO because of the potential for unblinding.

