Double-blind, Randomized Treatment Period (Visits 10 to 22): Following successful completion of titration, participants will be randomized 2:1 (lixivaptan: placebo) to continue to receive lixivaptan at the dose achieved at the end of the Lixivaptan Titration Period or to matching placebo in a double-blind fashion for 52 weeks. Study visits will be scheduled every 4 weeks during this period. Assessments at each visit are detailed in the [Schedule of Procedures – Part 1](#).

Follow-up Period I (Visits 23 to 25): Three visits will occur over a 28-day, study drug-free period following the last dose of study drug. Blood samples will be drawn at 3 time points for serum creatinine and serum cystatin C, to determine eGFR for primary and exploratory analyses, respectively. The first visit (Visit 23) will occur on the 8th day (+ 3 days) after the last dose of study drug, and the last visit (Visit 25) will occur on the 28th day (\pm 3 days) after the last dose of study drug. Visit 24 must be scheduled to occur at least 24 hours after Visit 23 and at least 24 hours prior to Visit 25. At Visit 25, additional efficacy and safety assessments will be performed; a post-baseline MRI for assessment of TKV and LV is to be obtained between 25 days and 31 days post last dose of study drug and must be completed prior to or on the same day as all other Visit 25 study procedures. Following completion of these assessments, all participants (except those who discontinued due to an AE or who have withdrawn consent) will immediately continue into Part 2 at Visit 25.

Note: In the event of tolerability issues at any time during the study, dosing may be decreased or temporarily stopped. If dosing is resumed during the Double-Blind Treatment Period at a dose level less than that achieved at Visit 9, attempts will be made every 4 to 8 weeks to re-establish the previously achieved dose level from Visit 9, if medically appropriate. If study drug is interrupted for longer than 8 weeks, then study drug treatment will be permanently discontinued.

Part 2:

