Lixivaptan Re-Titration Period (Visits 26 to 29): For all participants, titration of lixivaptan will occur over a 2 to 4-week re-titration period and will start at a dose of 50 mg BID beginning at the conclusion of Visit 25. The dose will be increased at weekly intervals until the dose level from the end of the Double-blind, Randomized Treatment Period in Part 1 is achieved. In order to maintain blinding of the treatment assignment from Part 1, the dose level assignment for Part 2 will continue to be managed by the IRT. The dose-titration schedule for this part of the study is described in [Table 2](#). In the event of tolerability issues,

dosing may be decreased. **Note:** during the Re-titration Period of Part 2, all participants are re-titrated with lixivaptan to the last actual dose level if they had received lixivaptan during the Double-blind, Randomized Treatment Period, or, if they had received placebo during the Double-blind, Randomized Treatment Period, to the last inferred dose level (the dose level equal to the active dose level had the participant been randomized to the active arm). Re-titration will be performed by the IRT, and the site, participant, and sponsor maintain a blinded status to the prior treatment assignment in Part 1. If no adjustment is made to the inferred dose during the Double-Blind, Randomized Treatment Period, the last inferred dose for a participant randomized to placebo will be equal to the maximal tolerated lixivaptan dose established during the Titration Period in Part 1.

Maintenance Treatment Period (Visits 30 to 42): Following completion of the Lixivaptan Re-titration Period, participants will continue to receive lixivaptan in the Maintenance Treatment Period for 52 weeks at the same dose achieved at the end of the Re-titration Period in Part 2. If the participant's dose was decreased during the Lixivaptan Re-Titration Period, attempts will be made every 4 to 8 weeks to re-establish the previously achieved dose level (actual or inferred) at the end of the Double-blind, Randomized Treatment Period of Part 1. Visits will be performed every 4 weeks during this period. Assessments at each visit are detailed in the [Schedule of Procedures – Part 2](#).

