For all efficacy analyses, the eGFR values will be calculated and rounded to 1 decimal based on equations and age defined above for analysis. However, the calculated eGFRs for efficacy analyses will not impact the determination of the randomization stratification factors.

11. Interim Analysis and Data Monitoring

Data analyses are planned to be conducted for Part 1 after the completion of Part 1 and unblinding of study after completion of Part 1. No interim analysis is planned for the efficacy analysis.

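### SAP 3.5 unblinds the trial at Part 1 database lock without limiting who is unblinded, which conflicts with the protocol and SAP rules that keep Part 1 assignment masked during Part 2

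*SAP*

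**What the plan says.** **Passages that lift the blind.** SAP 3.5 first names participants, investigators, site personnel and sponsor staff as blinded after randomization, with exceptions for the IDMC, its support and the SDAC. It then says: "The trial will be unblinded following the locking of the database in Part 1". Its next paragraph withholds post-randomization MRI volumes, urine osmolality and PK data "until the locking of the database in Part 1 of the study". SAP Section 11 plans the Part 1 analysis together with "unblinding of study after completion of Part 1". None of these passages limits the unblinding to a particular group.

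**Passages that keep it.** Protocol 3.1.2, on re-titration at the start of Part 2, says that "the site, participant, and sponsor maintain a blinded status to the prior treatment assignment in Part 1". SAP 3.6 carries the same sentence, and Protocol 6.6 says the same in substance. The protocol synopsis leaves Part 2 dosing to the IRT for the same reason; its sentence begins: "In order to maintain blinding of the treatment assignment from Part 1, the dose level assignment for Part 2 will continue to be". The Table 4 footnotes, which cover Part 2 only, say that MRI-derived data "will NOT be shared with the participant, the investigator, the clinical sites, the sponsor, or the CRO because of the potential for unblinding". They treat PK samples (Visits 29 to 38) and osmolality (Visits 29 to 45) in the same way. No end date is given for any of these rules.

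**List of changes.** SAP Section 15 sets out the departures from the protocol. The blind is not among them.

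**The concern.** After Visit 25 every participant who continues takes lixivaptan, so the only assignment left to protect in Part 2 is the Part 1 arm. The protocol goes to some trouble to protect it, through IRT dosing to an inferred level and through withheld results. SAP 3.5 removes that protection at a date when participants may be anywhere in Part 2.

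SAP 6.1.2 presents Part 2 by cohort (placebo then lixivaptan, or lixivaptan throughout) as well as overall. Some of what is presented that way depends on judgement or self-report: adverse events with investigator causality (SAP 9.2) and the three patient-reported scales (SAP 8.10). If site or participant learns the earlier arm midway, reporting can shift differently in the two cohorts, and so can willingness to stay. Each cohort would also mix people who finished Part 2 masked with people who did not.

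**Working it through.** **1. Length of Part 2.** Re-titration 2 to 4 weeks, maintenance 52 weeks and follow-up 4 weeks (Protocol Table 4): 2 + 52 + 4 = 58 and 4 + 52 + 4 = 60. This reproduces the 58 to 60 weeks in the synopsis.

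**2. Number entering Part 2.** 0.90 × 1350 = 1215, as the protocol states.

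**3. When lock falls relative to Part 2.** Participants "will immediately continue into Part 2 at Visit 25". Part 1 cannot be locked before the last Visit 25, so lock falls inside someone's Part 2 unless it comes more than 58 to 60 weeks after that visit.

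**4. Share still in Part 2 at lock.** The documents give neither the accrual period nor the lag to lock, so the following are assumptions: Visit 25 dates spread evenly over A weeks, lock L weeks after the last Visit 25, and no dropout in Part 2. A participant whose Visit 25 was t weeks before the last one is still in Part 2 at lock if t + L < D, where D is 58 or 60. The share is therefore min(1, (D − L)/A).

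For example, with L = 8: at A = 78, 50/78 = 64% and 52/78 = 67%; at A = 104, 50/104 = 48% and 52/104 = 50%.

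| A (weeks) | L = 4 | L = 8 | L = 12 | L = 26 |
|---|---|---|---|---|
| 52 | 1215 (100%) | 1168–1215 (96–100%) | 1075–1122 (88–92%) | 748–794 (62–65%) |
| 78 | 841–872 (69–72%) | 779–810 (64–67%) | 717–748 (59–62%) | 498–530 (41–44%) |
| 104 | 631–654 (52–54%) | 584–608 (48–50%) | 537–561 (44–46%) | 374–397 (31–33%) |
| 156 | 421–436 (35–36%) | 389–405 (32–33%) | 358–374 (29–31%) | 249–265 (21–22%) |

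**5. Does the masking rule cover only re-titration?** With L of 4 weeks or more, nobody is still in the nominal 2 to 4 week re-titration at lock: (4 − 4)/A = 0. If the rule covered only re-titration, it would have lapsed for everyone and there would be no conflict with the sentence in SAP 3.6. That reading does not account for Table 4, which withholds results at maintenance visits and at Visit 45, the last visit of the study. SAP 3.5 ends the hold on the same three kinds of data at Part 1 lock. Those two rules cannot both be followed for a participant who is in Part 2 at lock.

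**The case against.** The case on the other side has several parts, and some of it stands.

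- **Permission, not instruction.** A reader might infer that SAP 3.5 sends the assignments to participants and sites. It does not say so. It declares the trial unblinded and ends a prohibition, without naming recipients. The fault is an unlimited permission.
- **No stated end point.** A reader might also infer that the documents already promise masking until Part 2 lock. They do not. The masking sentence sits in re-titration text each time and has no end date. The support for a longer blind comes from Table 4 and from IRT control of the Part 2 dose level.
- **Table 4 largely repeats Table 3.** The wording is similar, and Part 2 lixivaptan concentrations would not show the earlier arm, since everyone is then on drug. This weakens the purpose of withholding Part 2 PK results but does not remove the rule. The Part 1 PK results released at lock would show the arm.
- **Limited consequence.** Part 2 is open-label and its efficacy comparisons are descriptive. Its key endpoints, creatinine-based eGFR and ALT, are laboratory values. Not every Part 2 summary is by original arm: SAP 9.7, for instance, summarises all participants together. All of this stands.
- **Moot in practice.** SAP Section 12 reports that 5 participants were randomized and all stopped in Part 1. Nobody reached Part 2. This stands too.

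**Conclusion.** The point holds as a conflict within the SAP (3.5 and 11 against 3.6) and between the SAP and the protocol (3.1.2, 6.6 and Table 4), not declared in SAP Section 15. It is more than missing detail, because following SAP 3.5 as written could expose the earlier arm during Part 2.

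On the plan as designed, about 48% to 67% of Part 2 participants would still be in Part 2 at lock, given uniform accrual over 18 to 24 months and an 8-week lag. The range is 21% to 100% for accrual of 52 to 156 weeks and lags of 4 to 26 weeks. A reader might instead divide 59 weeks by 78 or 104 and get 76% or 57%; that assumes lock on the day of the last Visit 25 and is too high for any realistic lag.

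The exposure is to adverse-event reporting and causality, symptom scales and retention. A threat to the primary result should not be inferred: the Part 1 hierarchy in SAP 6.1.3 is tested on data already locked, so type I error is unaffected. Priority is low, and for this terminated trial the practical effect is nil.

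**What to change.** In SAP 3.5 and Section 11, restrict unblinding at Part 1 lock to a named analysis and reporting team. State that participants, sites and Part 2 operational staff stay masked to Part 1 assignment until Part 2 lock, and that Part 2 MRI, PK and osmolality results stay withheld until then. Part 1 results of the same kind should stay within the named team, since they can reveal the arm. The end point has to be added, because neither document states one. Protocol 3.1.2 and SAP 3.6 also name the sponsor as blinded, so any sponsor access needed for Part 1 reporting should be listed in SAP Section 15.

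The cost is SAP wording, access control and a small firewall burden while Part 1 is reported. The Part 1 analysis need not wait for Part 2.
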